## 8 Visit schedule and assessments

The below Assessment Schedules ([Table 8-1](#), [Table 8-2](#), [Table 8-3](#), [Table 8-4](#), [Table 8-5](#) and [Table 8-6](#)) list all assessments with an X when they are performed. All data obtained from these assessments must be supported in the participant's source documentation. The "X" in the table denotes the assessments to be recorded in the clinical database or received electronically from a vendor. The "S" in the table denotes the assessments that are only in the participant's source documentation and do not need to be recorded in the clinical database.

Participants should be seen for all visits/assessments as outlined in the assessment schedules or as close to the designated day/time as possible. The Investigator should promote compliance by instructing the participant to attend the study visits as scheduled and by stating that compliance is necessary for the participant's safety and the validity of the study. Missed or rescheduled visits should not lead to automatic discontinuation. The participant should be instructed to contact the Investigator if he/she is unable for any reason to attend a study visit as scheduled or if he/she is unable for any reason to take the study treatment as prescribed.

Participants who prematurely discontinue the study should be scheduled for the End of Study (EOS) visit within 7 days. At this final visit, all the assessments mentioned under EOS visit should be performed, all dispensed investigational product should be reconciled, and the

adverse event and concomitant medications recorded on the CRF. Participants that prematurely discontinue should also have a remote follow-up safety visit performed 30 days after the EOS visit.

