### **Special guidance regarding the scheduling of visits for Cohorts 1, 2 and 3**

- The study site will need to perform Vaccine Status Check-ins (make remote contact with participant) to confirm when the 1st and 2nd COVID-19 vaccinations are scheduled in order to schedule Visit 4.
- The date of the 2nd COVID-19 vaccine dose will determine the date of Visit 4 and all other remaining study visits.
- Visits 2 and 3 should always occur prior to administration of the mRNA vaccine.
- The Visit 4 lab samples should be collected 14 days after a participant has received their 2nd COVID-19 vaccine dose.

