Cohort 2: Relapsing MS participants receiving a full course (2 doses) of a non-live COVID-19 mRNA vaccine ≥4 weeks after ofatumumab start.

Will continue taking their prescribed ofatumumab as per their current dosing schedule.

Cohort 3: Relapsing MS participants receiving a full course (2 doses) of a non-live COVID-19 mRNA vaccine ≥4 weeks after start of prescribed interferon or glatiramer acetate.

Will continue administration of their prescribed interferon or glatiramer acetate as per their current dosing schedule.

Cohort 4: Relapsing MS participants having completed a full course (2 doses) of a non-live COVID-19 mRNA vaccine ≥4 weeks after ofatumumab start.

Will continue taking their prescribed ofatumumab as per their current dosing schedule.

Cohort 5: Relapsing MS participants having completed a full course (2 doses) of a non-live COVID-19 mRNA vaccine ≥4 weeks after glatiramer acetate or interferon start.

Will continue taking their prescribed glatiramer acetate or interferon as per their current dosing schedule.

Cohort 6: Relapsing MS participants having completed a full course (2 doses) of a non-live COVID-19 mRNA vaccine ≥4 weeks after ofatumumab start and having received a booster ≥14 days prior to screening.

Will continue taking their prescribed ofatumumab as per their current dosing schedule.

Study completion

According to the protocol, study completion is defined as when the last participant completes the end of study (EOS) visit. Participants who discontinue study treatment or who decide they do not wish to participate in the study further should NOT be considered withdrawn from the study UNLESS they withdraw their consent. Where possible, they should return for the EOS visit.

Study design schematics for Cohorts 1, 2 and 3 are shown in Figures 1, 2, 3 and 4. Study design schematics for Cohorts 4, 5 and 6 are shown in Figures 5 and 6.

Figure 1 Study Design (Cohort 1, Pfizer)

[figure not shown]

Figure 2 Study Design (Cohort 1, Moderna)

[figure not shown]

Figure 3 Study Design (Cohorts 2 and 3, Pfizer)

[figure not shown]

Figure 4 Study Design (Cohorts 2 and 3, Moderna)

[figure not shown]

Figure 5 Study Design (Cohorts 4, 5 and 6, Pfizer)

[figure not shown]
[figure not shown]

Figure 6 Study Design (Cohorts 4, 5 and 6, Moderna)

Primary analysis time point

The primary analysis time point is Visit 4 for Cohorts 1, 2 and 3, and Visit 2 for Cohorts 4, 5 and 6.

Interim analysis

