2.4.1.1 Visit windows

Visit windows will be used for data that are summarized by visit; they are based on the study evaluation schedule and comprise a set of days around the nominal visit day. When visit windows are used, all visits, including unscheduled visits, will be re-aligned (i.e., they will be mapped into one of the visit windows). In the case of major deviations from the visit schedule, or due to unscheduled visits, several assessments for a participant may fall in a particular visit window (either scheduled or unscheduled). Approaches for handling multiple assessments in a visit window are outlined below.

The following steps are used to determine the cut-offs for visit windows:

- The visit window associated with the previous assessment ends prior to the middle point; the visit window associated with the latter assessment begins after the middle point. In case the middle point is an exact study day, it will belong to the previous assessment.
- The visit window of the first post-vaccination assessment starts the day after the second dose of the COVID-19 vaccine for Cohorts 1 – 5, and the day after the COVID-19 vaccine booster for Cohort 6, unless otherwise specified.

Tables 2 – 10 provide visit windows for applicable parameters.

Table 2**Cohort 1 visit windows for SARS-CoV-2 qualitative antibody / CD19+ B cells / T cell**

Analysis visit	Nominal time point	Scheduled visit day (target study day)	Visit window (study days)
Pfizer vaccine:			
Pre-vaccination	Day 1	1	≤1
14 days post-vaccination	Day 36	36	(vaccine day + 1) to 64
70 days post-vaccination	Day 92	92	65 to 147
180 days post-vaccination	Day 202	202	148 to 247
270 days post-vaccination	Day 292	292	248 to 337
360 days post-vaccination	Day 382	382	≥338
Moderna vaccine:			
Pre-vaccination	Day 1	1	≤1
14 days post-vaccination	Day 43	43	(vaccine day + 1) to 71
70 days post-vaccination	Day 99	99	72 to 154
180 days post-vaccination	Day 209	209	155 to 254
270 days post-vaccination	Day 299	299	255 to 344
360 days post-vaccination	Day 389	389	≥345

Note:

- Pre-vaccination and study day are derived as outlined in [Section 2.1.1](#).
- Vaccine day is the study day of the second dose of the COVID-19 vaccine.
- Assessments performed between the first and second doses of the COVID-19 vaccine are not assigned an analysis visit.

Table 3**Cohort 1 visit windows for serum immunoglobulin (IgG, IgM)**

Analysis visit	Nominal time point	Scheduled visit day (target study day)	Visit window (study days)

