Pfizer vaccine:			
Pre-vaccination	Day 1	1	≤1
14 days post-vaccination	Day 36	36	(vaccine day + 1) to 64
70 days post-vaccination	Day 92	92	65 to 147
180 days post-vaccination	Day 202	202	148 to 292
360 days post-vaccination	Day 382	382	≥293
Moderna vaccine:			
Pre-vaccination	Day 1	1	≤1
14 days post-vaccination	Day 43	43	(vaccine day + 1) to 71
70 days post-vaccination	Day 99	99	72 to 154
180 days post-vaccination	Day 209	209	155 to 299
360 days post-vaccination	Day 389	389	≥300

Note:

- Pre-vaccination and study day are derived as outlined in [Section 2.1.1](#).
- Vaccine day is the study day of the second dose of the COVID-19 vaccine.
- Assessments performed between the first and second doses of the COVID-19 vaccine are not assigned an analysis visit.

[figure not shown]

Table 5**Cohorts 2 and 3 visit windows for SARS-CoV-2 qualitative antibody / CD19+ B cells (Cohort 2 only) / T cell**

Analysis visit	Nominal time point	Scheduled visit day (target study day)	Visit window (study days)
Pfizer vaccine:			
Pre-vaccination	Day 1	1	≤1
14 days post-vaccination	Day 36	36	(vaccine day + 1) to 119
180 days post-vaccination	Day 202	202	120 to 247
270 days post-vaccination	Day 292	292	248 to 337
360 days post-vaccination	Day 382	382	≥338
Moderna vaccine:			
Pre-vaccination	Day 1	1	≤1
14 days post-vaccination	Day 43	43	(vaccine day + 1) to 126
180 days post-vaccination	Day 209	209	127 to 254
270 days post-vaccination	Day 299	299	255 to 344
360 days post-vaccination	Day 389	389	≥345

Note:

- Pre-vaccination and study day are derived as outlined in [Section 2.1.1](#).
- Vaccine day is the study day of the second dose of the COVID-19 vaccine.
- Assessments performed between the first and second doses of the COVID-19 vaccine are not assigned an analysis visit.

Table 6**Cohorts 2 and 3 visit windows for serum immunoglobulin (IgG, IgM)**

Analysis visit	Nominal time point	Scheduled visit day (target study day)	Visit window (study days)
Pfizer vaccine:			
Pre-vaccination	Day 1	1	≤1
180 days post-vaccination	Day 202	202	(vaccine day + 1) to 292
360 days post-vaccination	Day 382	382	≥293
Moderna vaccine:			
Pre-vaccination	Day 1	1	≤1
180 days post-vaccination	Day 209	209	(vaccine day + 1) to 299
360 days post-vaccination	Day 389	389	≥300

Note:

- Pre-vaccination and study day are derived as outlined in [Section 2.1.1](#).
- Vaccine day is the study day of the second dose of the COVID-19 vaccine.

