 - For *continuous variables*, the assessment with the study day that is closest to the target study day is selected. If two assessments are equidistant from the target study

day, the earlier assessment is selected (if one of the two equidistant assessments is an unscheduled assessment, it should be excluded from consideration).

- For *categorical variables*, the assessment with the worst result is selected.

If categorical variables are based on continuous variables, the analysis visit will be assigned to the continuous variable, and this analysis visit will be used for the derived categorical variable.

In situations where the same assessment is performed more than once on the same date the repeated assessment will be used.

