2.5.1 Primary endpoint(s)

The primary endpoint is achieving immune response as defined by a positive SARS-CoV-2 qualitative IgG antibody assay ≥ 14 days after full course (2 doses) vaccination (yes/no).

The primary estimand is described by the following attributes:

- **Population:** Defined through appropriate inclusion/exclusion criteria to reflect the targeted population. Relapsing MS participants subdivided into 6 cohorts. (1) Will receive a full course (2 doses) of a COVID-19 mRNA vaccine ≥ 2 weeks prior to starting ofatumumab 20 mg s.c. treatment; (2) Will receive a full course (2 doses) of a COVID-19 mRNA vaccine after ≥ 4 weeks of commercial ofatumumab 20 mg s.c. treatment (3) Will receive a full course (2 doses) of a COVID-19 mRNA vaccine after ≥ 4 weeks of interferon or glatiramer acetate treatment (4) Completed a full course (2 doses) of a COVID-19 mRNA vaccine after ≥ 4 weeks of commercial ofatumumab 20 mg s.c. treatment but has not yet received a COVID-19 mRNA booster (5) Completed a full course (2 doses) of a COVID-19 mRNA vaccine after ≥ 4 weeks of interferon or glatiramer acetate (may or may not have received a COVID-19 mRNA booster) (6) Completed a full course (2 doses) of a COVID-19 mRNA vaccine after ≥ 4 weeks of commercial ofatumumab 20 mg s.c. treatment and received an additional booster vaccine ≥ 14 days prior to screening
- **Variable:** Achieving immune response as defined by a positive SARS-CoV-2 qualitative IgG antibody assay ≥ 14 days after full course (2 doses) vaccination (yes/no)
- **Treatment of interest:** Non-live COVID-19 mRNA vaccine either ≥ 2 weeks prior to ofatumumab start or ≥ 4 weeks after ofatumumab start or while on interferon or glatiramer acetate
- **Intercurrent event:** Discontinuation of treatment/study, or death
- **Summary measure:** Proportion of participants achieving immune response

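### The SAP's 14-day antibody windows in Cohorts 1–3 admit draws 1–13 days after dose 2 that fail the primary endpoint, and its later visit labels for Cohorts 4–6 understate time since the qualifying dose

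*SAP*

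**What the plan says.** **Endpoint.** SAP 2.5.1 defines response as a "positive SARS-CoV-2 qualitative IgG antibody assay ≥ 14 days after full course (2 doses) vaccination (yes/no"). SAP 1.1 adds: "The primary analysis time point is Visit 4 for Cohorts 1, 2 and 3, and Visit 2 for Cohorts 4, 5 and 6". Protocol Table 2-1 and section 2.1 also use the at-least form. The data-analysis entry of the protocol summary and Protocol 12.4.1 say 14 days with no ≥ sign.

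**Windows.** SAP 2.4.1.1 sets the opening rule for Cohorts 1–5: "The visit window of the first post-vaccination assessment starts the day after the second dose of the COVID-19 vaccine". A general saving clause follows, but nothing is then specified for the primary endpoint. In SAP Table 5 the 14-day row for Cohorts 2 and 3 (Pfizer) runs from ("vaccine day + 1) to 119". Table 2 does the same for Cohort 1, ending at Day 64 (Pfizer) or Day 71 (Moderna). Unscheduled visits are mapped into windows too.

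**Several assays in one window.** For categorical variables, "the assessment with the worst result is selected". There is an exception: "If categorical variables are based on continuous variables, the analysis visit will be assigned to the continuous variable". The SAP does not say which case the qualitative assay falls under.

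**Timing of the draw.** Protocol section 8, special guidance for Cohorts 1–3: "The Visit 4 lab samples should be collected 14 days after a participant has received their" second dose. The Visit 4 tolerance is ±3 days for Cohort 1 (Tables 8-1 and 8-2) and +3 days only for Cohorts 2 and 3 (Tables 8-3 and 8-4).

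**Cohorts 4–6.** Study day counts from Visit 2. Entry requires at least two weeks since dose 2 (Cohorts 4 and 5) or the booster (Cohort 6), with no upper limit. SAP Table 8 nevertheless labels the later visits 180, 270 and 360 days post-vaccination, and Table 9 uses 180 and 360 for immunoglobulins. Protocol 8.5.2 gives the Cohort 4 and 6 immunoglobulin times as ≥180 and ≥360 days.

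**The concern.** For Cohorts 1–3 the SAP holds two timing rules for one primary endpoint. One programmer could follow the window tables, the responder definition in SAP 2.5 (which says only after the full course) and the imputation trigger in SAP 5.1.3.3 (no valid assessment after both doses), and would count a positive on day 12. Another could follow SAP 2.5.1 and the next sentence of 5.1.3.3, which restates the 14-day minimum, and would impute No unless a later assay qualified. SAP section 4 declares no change from the protocol, so it does not settle the matter. The trial tests no hypothesis: the response rate and its exact interval are the result, and they should not depend on which paragraph was read.

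For Cohorts 4–6 the issue is reporting. The labels state times since vaccination that on-schedule visits do not have when measured from the qualifying dose. SAP 2.1 then pools Cohort 4 with Cohort 2, and Cohort 5 with Cohort 3, so one sustained-response row mixes different elapsed times. SAP 2.4.1 plans summaries of time from the start of MS treatment, but none of time since the last vaccine dose.

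**Working it through.** **1. Reproduce the plan's labels in Cohorts 1–3.** Inputs: dose 2 on Day 22 (Pfizer) or Day 29 (Moderna), and the target days in SAP Table 2. Elapsed days = target − dose-2 day.

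- Pfizer: 36, 92, 202, 292, 382 minus 22 = 14, 70, 180, 270, 360.
- Moderna: 43, 99, 209, 299, 389 minus 29 = 14, 70, 180, 270, 360.

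The labels are exact here. Table 5 uses the same targets without the 70-day visit.

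**2. Span of the 14-day window in days after dose 2, on schedule.** It opens at day 1 by rule.

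| | Pfizer | Moderna | Span |
|---|---|---|---|
| Cohort 1 | 64 − 22 = 42 | 71 − 29 = 42 | 1–42 |
| Cohorts 2, 3 | 119 − 22 = 97 | 126 − 29 = 97 | 1–97 |

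Days 1–13 of each span fail the endpoint.

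**3. Which draws can fall there?**

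- Cohort 1, Visit 4 at ±3 days: 36 − 3 − 22 = 11 to 36 + 3 − 22 = 17 (Pfizer); 43 − 3 − 29 = 11 to 43 + 3 − 29 = 17 (Moderna). Days 11, 12 and 13 are too early. The tolerance is clear in Table 8-1 and in the second part of Table 8-2; the first part of Table 8-2 is less clear in the text available.
- Cohorts 2 and 3, +3 days only: days 14 to 17. No in-tolerance visit is early.
- Other routes need an extra or off-schedule draw, such as an early end-of-study visit: "Participants who prematurely discontinue the study should be scheduled for the End of Study (EOS) visit within 7 days". The worst-or-nearest question also arises only with extra draws, because Visit 4 is the only scheduled antibody draw in this window.
- A correct day-14 draw leaves the window only if dose 2 is more than 64 − 14 − 22 = 28 days late in Cohort 1, or 119 − 14 − 22 = 83 days late in Cohorts 2 and 3. Moderna gives the same values.

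**4. Effect on the rate.** One participant is 1/22 = 4.5 points. The documents give no frequency of early draws. As an assumption, let k of 22 Cohort 1 participants have only a positive assay on days 11–13, with 16 responders if these count. Intervals are exact 95%.

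| k | Counted | Imputed No | Observed case |
|---|---|---|---|
| 0 | 16/22 = 72.7% (49.8–89.3) | no change | no change |
| 1 | 16/22 = 72.7% | 15/22 = 68.2% (45.1–86.1) | 15/21 = 71.4% (47.8–88.7) |
| 3 | 16/22 = 72.7% | 13/22 = 59.1% (36.4–79.3) | 13/19 = 68.4% (43.4–87.4) |

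**5. Labels in Cohorts 4–6.** Earliest on-schedule elapsed time from the qualifying dose = target − 3 (tolerance) − 1 (Visit 2 is Day 1) + 14 (minimum lag).

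- Pfizer: 202, 292, 382 give 212, 302, 392, which is 32 days beyond each label.
- Moderna: 209, 299, 389 give 219, 309, 399, which is 39 days beyond each label.

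These are minimums, because the lag has no upper limit.

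**The case against.** The strongest reply is that the endpoint definition already acts as a filter, so the windows merely sort visits. That reading is sensible, but the SAP does not state it, and its responder definition and imputation trigger can be read the other way.

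A reader might infer that the protocol freely permits three of the seven Cohort 1 Visit 4 days (11–17) before day 14, and so that a large share of samples is at risk. The documents do not support this. The early days rest on the tolerance row alone. Cohort 1 inclusion criterion 5, Protocol 6.1.3 and 6.3.2, the special visit guidance and SAP 1.1 all point to two weeks or more, and a count of days is not a frequency.

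It is also tempting to say that the protocol uniformly demands at least 14 days. It does not: its summary and section 12.4.1 say 14 days, under which a day 11–13 draw could pass as the nominal sample. This is part of what needs reconciling.

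On the labels, it is fair to say that relabelling changes no response rate, and that Table 8 prints study days and defines the vaccine day. Three limits also stand. Eligibility secures the 14-day minimum at the primary visit in Cohorts 4–6. Cohort 6 is reported alone, so only Cohorts 4 and 5 are pooled under shared labels. Protocol 12.5 foresees boosters during the trial, so time since the latest vaccination could match a label by chance; the error is relative to the qualifying dose in the table's own footnote.

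**Conclusion.** Both parts hold, within limits. In Cohorts 1–3 the stated window rule conflicts with the SAP's primary endpoint for draws 1–13 days after dose 2, and nothing ranks the two rules. The exposure is mainly Cohort 1 on days 11–13. Its frequency is unknown and probably small, and with no early draws nothing changes. Each affected participant is worth 4.5 points at n = 22; the larger shifts in the table depend on the assumed k and the assumed 16/22. The documents do not support a claim that the primary results are materially biased.

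In Cohorts 4–6 the later labels understate time since the qualifying dose by at least 32 days (Pfizer) or 39 days (Moderna) at any on-schedule visit. This affects how durability is described, not the primary estimate. Both points should be fixed because the correction is cheap and the response rate is the trial's main result.

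**What to change.** 1. In SAP Tables 2 and 5, open the primary antibody window at vaccine day + 14 and keep the present upper bounds. On schedule this is days 14–42 after dose 2 in Cohort 1 and days 14–97 in Cohorts 2 and 3.
2. Use the Visit 4 assay or, failing that, the eligible assay nearest day 14, in place of the worst result.
3. State in SAP 2.5.3 and 5.1.3.3 that non-response imputation applies when no valid assay lies in this window.
4. Report how many Cohort 1 draws fell on days 11–13. Give the primary result without them as the main row and with them, as observed, in a second row. The planned observed-case analysis does not replace the second row, because under the at-least-14-day rule it drops these draws from the denominator.
5. Reconcile the Cohort 1 Visit 4 tolerance, and the two endpoint wordings, across the protocol summary, Table 2-1, sections 2.1, 5.1, 6.1.3, 6.3.2, 8 (special guidance, Tables 8-1 and 8-2) and 12.4.1, and SAP 1.1. No clinical rule is proposed here.
6. Label Cohort 4–6 visits by time from enrolment, or as ≥ minimums as Protocol 8.5.2 does, and tabulate days since the last vaccine dose at the primary sample by individual cohort.

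The cost is SAP wording, re-derivation of analysis visits from dates already collected, and a few table rows. The drawback is that an observed positive on days 11–13 becomes No in the main row when no later assay is in the window; the second row makes that visible.

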## Remote procedures

At the investigator's direction and based on benefit-risk considerations of the participant's clinical condition, qualifying participants may be offered the option to have certain clinical trial procedures according to the assessment schedules in [Table 8-1](#), [Table 8-2](#), [Table 8-3](#), [Table 8-4](#), [Table 8-5](#) and [Table 8-6](#) performed from within their home.

Such procedures will be performed remotely under the oversight of the Investigator, who retains accountability for the oversight and all efficacy and safety decisions with delegation of tasks to an off-site healthcare professional. Off-site healthcare professionals will be provided by a third-party vendor sourced by Novartis or an agent for Novartis.

In addition to procedures performed by the off-site healthcare professional, the on-site staff may perform certain procedures remotely using tele-visits.

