- Assessments performed between the first and second doses of the COVID-19 vaccine are not assigned an analysis visit.

Table 8**Cohorts 4, 5 and 6 visit windows for SARS-CoV-2 qualitative antibody / CD19+ B cells (Cohorts 4 and 6 only) / T cell**

Analysis visit	Nominal time point	Scheduled visit day (target study day)	Visit window (study days)
Pfizer vaccine:			
14 days post-vaccination	Day 1	1	(vaccine day + 1) to 1
180 days post-vaccination	Day 202	202	2 to 247
270 days post-vaccination	Day 292	292	248 to 337
360 days post-vaccination	Day 382	382	≥338
Moderna vaccine:			
14 days post-vaccination	Day 1	1	(vaccine day + 1) to 1
180 days post-vaccination	Day 209	209	2 to 254
270 days post-vaccination	Day 299	299	255 to 344
360 days post-vaccination	Day 389	389	≥345

Note:

[figure not shown]
- Study day is derived as outlined in [Section 2.1.1](#).
- Vaccine day is the study day of the second dose of the COVID-19 vaccine for Cohorts 4 and 5, and the study day of the COVID-19 vaccine booster for Cohort 6.

Table 9 **Cohorts 4, 5 and 6 visit windows for serum immunoglobulin (IgG, IgM)**

Analysis visit	Nominal time point	Scheduled visit day (target study day)	Visit window (study days)
Pfizer vaccine:			
14 days post-vaccination	Day 1	1	(vaccine day + 1) to 1
180 days post-vaccination	Day 202	202	2 to 292
360 days post-vaccination	Day 382	382	≥293
Moderna vaccine:			
14 days post-vaccination	Day 1	1	(vaccine day + 1) to 1
180 days post-vaccination	Day 209	209	2 to 299
360 days post-vaccination	Day 389	389	≥300

Note:

- Study day is derived as outlined in [Section 2.1.1](#).
- Vaccine day is the study day of the second dose of the COVID-19 vaccine for Cohorts 4 and 5, and the study day of the COVID-19 vaccine booster for Cohort 6.

Multiple assessments

When there are multiple assessments in a particular visit window, the rules outlined below are applied to select one value “representing” the participant in summary statistics for that visit window. All assessments will be displayed in listings.

- **Pre-vaccination (only applicable to Cohorts 1, 2 and 3):** Pre-vaccination is derived as outlined in [Section 2.1.1](#). In situations where the same assessment is performed more than once on Study Day 1 the repeated assessment will be used.
- **Post-vaccination:** For post-vaccination visit windows, the following rules apply (unless otherwise specified):

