2.5.3 Handling of intercurrent events

Non-response imputation (NRI) approach will be applied to missing post-vaccination antibody assay regardless of intercurrent events.

NRI is a conservative imputation method for dichotomous variables. NRI assumes that a participant is a treatment failure if the participant discontinues the study prematurely. Hence, for missing data the primary endpoint will be imputed as “No”. Refer to [Section 5.1.3.3](#).

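### SAP Tables 8 and 9 open the 180-day window for Cohorts 4–6 on Day 2, against the SAP's own midpoint rule, so early samples are reported as 180-day results

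*SAP*

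**What the plan says.** SAP 2.4.1.1 gives one rule for the boundary between consecutive windows: "The visit window associated with the previous assessment ends prior to the middle point", and the later window begins after it. Ties are settled: "In case the middle point is an exact study day, it will belong to the previous assessment". A separate bullet fixes only where the first window begins: "The visit window of the first post-vaccination assessment starts the day after the second dose of the COVID-19 vaccine for Cohorts 1 – 5", or the day after the booster for Cohort 6. The allowance for other specifications is attached to that bullet, not to the midpoint rule. The windows also catch off-schedule samples, because "all visits, including unscheduled visits, will be re-aligned".

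Table 8 (antibody assay and B cells) and Table 9 (serum immunoglobulin) cover Cohorts 4–6. Both print the first window as "vaccine day + 1) to 1" for both vaccines. The next window has target Day 202 (Pfizer) or Day 209 (Moderna) and starts on Day 2. By contrast, Table 5 prints the first Pfizer window for Cohorts 2 and 3 as "vaccine day + 1) to 119".

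Four other provisions matter:

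- SAP 1.1 sets Visit 2 as the primary time point for Cohorts 4–6, and SAP 2.1.1 defines Study Day 1 as the date of Visit 2.
- When several categorical results fall in one window, SAP 2.4.1.1 takes the worst.
- SAP 2.5.3 and 2.5.4 impute non-response when the post-vaccination assay is missing: "Hence, for missing data the primary endpoint will be imputed as “No". SAP 2.6.3 and 2.6.4 do the same for the secondary endpoints. SAP 5.1.3.3, to which 2.5.3 refers, makes a participant a non-responder when no valid assessment exists after both doses.
- Protocol section 8 brings early leavers in for an end-of-study visit within 7 days. Protocol Tables 8-5 and 8-6 include the antibody assay at that visit.

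**The concern.** The windows decide which sample represents a participant at each time point. With a boundary at Day 1/Day 2, a sample taken one day after Visit 2 shares a time point with one taken about 200 days later.

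The sustained-response endpoint is the most exposed. Someone in Cohorts 4–6 who leaves at, say, Day 20 with a positive end-of-study assay would be counted as a 180-day responder, when no sample near Day 202/209 exists and the SAP would otherwise impute non-response. For a participant who stays, an unscheduled negative in the first weeks would displace a later positive.

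The primary endpoint is exposed conditionally. The first window has no tolerance after Visit 2, so a valid later sample cannot fill a missing Day 1 result if missingness is judged within the window.

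The pooled groups (Cohorts 2 and 4, Cohorts 3 and 5) also mix two rules. Table 5 lets the first window run 119 − 36 = 83 days past target (Moderna 126 − 43 = 83); Table 8 allows 0 days.

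**Working it through.** **Rule.** For consecutive target days a and b, m = (a + b)/2. The earlier window ends at m rounded down to a whole day, and the later one starts the next day. Targets and printed limits come from SAP Tables 2, 3, 5, 6, 8 and 9, the ones visible in the public version.

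**Reproducing the SAP's cut-offs.**

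| Tables | Pfizer midpoint | Printed | Moderna midpoint | Printed |
|---|---|---|---|---|
| 2, 3 | (36+92)/2 = 64 | 64 | (43+99)/2 = 71 | 71 |
| 2, 3 | (92+202)/2 = 147 | 147 | (99+209)/2 = 154 | 154 |
| 5 | (36+202)/2 = 119 | 119 | (43+209)/2 = 126 | 126 |
| 2, 5, 8 | (202+292)/2 = 247 | 247 | (209+299)/2 = 254 | 254 |
| 2, 5, 8 | (292+382)/2 = 337 | 337 | (299+389)/2 = 344 | 344 |
| 3, 6, 9 | (202+382)/2 = 292 | 292 | (209+389)/2 = 299 | 299 |
| 8, 9 (first) | (1+202)/2 = 101.5, so 101 | **1** | (1+209)/2 = 105 | **1** |

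Counted by table and vaccine there are 8 + 6 + 6 + 2 + 6 + 4 = 32 cut-offs. Of these, 28 reproduce exactly, including every later cut-off in Tables 8 and 9. The four failures are the first cut-offs of Tables 8 and 9. They fall 101 − 1 = 100 days (Pfizer) and 105 − 1 = 104 days (Moderna) too early.

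**Where a sample goes.**

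- *Early leaver, end-of-study antibody sample on Day 20.* Printed Table 8: 180-day window. Midpoint rule: first window, with the 180-day result missing and imputed as non-response.
- *Unscheduled negative between Day 2 and Day 101/105, positive on Day 202/209.* Printed Table 8: both fall in the 180-day window and the worst result, taken to be the negative, is used. Midpoint rule: the Day 202/209 result stands.
- *No usable Visit 2 result, valid sample on Day 2 or later and at least 14 days after dose 2.* It satisfies the endpoint wording in SAP 2.5.1 but falls outside the first window. If 2.5.3/2.5.4 are applied by window, the result is non-response. If 5.1.3.3 is applied, a valid assessment exists and nothing is imputed.

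**Size per participant.** Each pooled group, and Cohort 6, is planned at 22, so one reclassified participant moves the proportion by 1/22 = 4.5 percentage points. For illustration, 18/22 = 81.8% (exact 95% CI 59.7 to 94.8) becomes 17/22 = 77.3% (54.6 to 92.2). At 180 days the shift can go either way: upward for an early leaver with a positive sample, downward when a negative displaces a later positive.

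**The case against.** The Day 1 limit may be deliberate. The SAP fixes the primary time point for these cohorts at Visit 2, and its change log says the windows were revised after the protocol amendment and a review of data. That could explain closing the first window at Visit 2. It does not explain starting the 180-day window the next day, and no exception is written.

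A reader might infer that a redrawn Visit 2 sample will be scored as non-response in the primary analysis. The documents do not support that as a certainty, and here the objection stands:

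- SAP 5.1.3.3 can be read to keep a participant with a valid later sample out of the imputation. The SAP does not say which reading governs.
- The documents describe no redraw after Visit 2. The protocol says that "qualifying participants may be offered the option to have certain clinical trial procedures" at home, but not on a date other than the visit. Because Visit 2 defines Day 1, an on-schedule sample or a same-day repeat is always inside the window.
- Table 9 concerns serum immunoglobulin and cannot affect the primary endpoint.

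Nor should the reach of the tables be taken as the number harmed. They could govern at most 22 + 44 = 66 of 88 participants, and only if Cohorts 2 and 3 enrolled nobody. Protocol Tables 8-5 and 8-6 list no antibody assay at unscheduled visits, so such samples may be few. All assessments remain visible in listings.

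Finally, widening the first window has a price: a primary result could come from a late sample, possibly after an on-study booster, and the worst-result rule could let a later negative replace a positive Visit 2 result. The fix has to deal with both.

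**Conclusion.** The first cut-offs in Tables 8 and 9 contradict the SAP's rule and should be corrected. The misfiling of early samples as 180-day results follows directly from the tables, and early end-of-study visits give it a route the protocol itself provides. The scoring of a valid later sample as non-response at the primary time point is possible, through Table 8 only, and depends on an ambiguity between 2.5.3/2.5.4 and 5.1.3.3.

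The effect is 4.5 percentage points per participant in a group of 22; how many participants are affected cannot be derived from the documents. The displacement of a positive Day 202/209 result assumes that the qualitative assay is handled as a categorical variable in its own right and that negative counts as worst. If it were derived from a quantitative value, SAP 2.4.1.1 would select the sample closest to target instead. The early-leaver effect does not depend on that assumption.

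**What to change.** 1. In Tables 8 and 9, end the first window on Day 101 (Pfizer) and Day 105 (Moderna), and start the 180-day window on Day 102 and Day 106.
2. For the primary result in Cohorts 4–6, use the Visit 2 assay. If it is missing, use the valid assay closest to Visit 2 within the first window that is at least 14 days after dose 2 (Cohort 6: after the booster) and before any booster received on study. State this as an exception to the worst-result rule.
3. Align 2.5.3 and 2.5.4 with 5.1.3.3, so that non-response is imputed only when no such assay exists.

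The cost is four cells in each of two tables and a few sentences, with no new data. The downside is small: a few primary results may come from samples drawn some weeks after Visit 2, at the extreme on Day 101 or 105. Table 5 already allows a comparable delay for Cohorts 2 and 3.
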